4.9 Efficacy Analysis

All efficacy analysis will be summarized by DL or arm for each phase primarily based on efficacy evaluable analysis set.

4.9.1 Tumor Assessment and Overall Visit Response

Initial tumor imaging at Screening must be performed within 28 days prior to the date of treatment. The first on-study imaging assessment should be performed at 6 weeks (± 1 week) from the date of the first study treatment. Subsequent tumor imaging should be performed every 6 weeks (± 1 week) or more frequently if clinically indicated. After the first 6 months, subjects who remain on treatment will have imaging performed every 9 weeks (± 1 week). Imaging should continue to be performed until disease progression is identified by the investigator, or notification by the Sponsor, whichever occurs first.

Target lesion response, non-target lesion response, and overall response of each visit will be reported by investigator according to RECIST 1.1 criteria and iRECIST criteria in protocol Appendix A.

The RECIST 1.1 assessment has the following possible response categories: CR, PR, SD, PD or NE.

The iRECIST criteria is similar to RECIST 1.1 but requires an evaluation of PD to be confirmed at subsequent assessment. For purposes of iRECIST assessment, the first visit showing PD according to RECIST 1.1 will be assigned as immune-unconfirmed PD (iUPD) at this visit. On a subsequent confirmatory imaging, the subject will be classified as progression confirmed (with an overall response of iCPD, see protocol Appendix A for the confirmation rules for iCPD). The iRECIST assessment has the following possible response categories: iCR, iPR, immune-Stable Disease (iSD), iUPD, iCPD, and NE.

4.9.2 Best Overall Response

BOR will be derived based on all overall visit response per subject.

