### 2.3. Study Rationale

Cancer patients commonly suffer from lymphopenia, stemming either from their disease or therapeutic interventions, such as chemotherapy and/or radiotherapy. This cancer-associated lymphopenia correlates with decreased overall survival (39). IL-7 has been shown to increase TCR repertoire in subjects by (1) expanding naïve T cell pools (40) and (2) supporting subdominant T cell clones and improving the survival of the CD8 memory pool (41). In addition to reversing lymphopenia, IL-7 has also been shown to enhance the functionality of effector T cells (42) and to antagonize the immunosuppressive effects of Tregs and MDSCs (43). Based on these various mechanisms, IL-7 administration may significantly augment PD-1/PD-L1 blockade by virtue of increasing the number and effector function of tumor infiltrating lymphocytes.

Hence, based on the mechanism of action for NT-I7 and the data obtained from preclinical and clinical studies, adding NT-I7 to a PD-1 inhibitor, such as pembrolizumab, will potentially a) convert an immunologically “cold” tumor to a “hot” tumor; b) make a tumor that has developed resistance to a PD-1/PD-L1 inhibitor to become responsive again; and c) enhance the anti-tumor activity in immunologically “warm” tumors. In this clinical study, CPI treated R/R TNBC, NSCLC, and SCLC are selected to test the hypothesis of whether adding NT-I7 could convert these tumors which have developed resistance to a CPI to become responsive to a CPI again. CPI naïve MSS-CRC and PC are selected to test the hypothesis of whether adding NT-I7 could convert these immunologically “cold” tumors into “hot” tumors. In addition, CPI naïve OC is added to test whether NT-I7 could enhance the limited anti-tumor activity of single-agent CPI in these tumor types.

Emerging data from Arms IV and V in this trial have shown promising results, comparable to recently presented data from MSS-CRC subjects given pembrolizumab in combination with favelzelimab, in which ORR was 6.3% (5/80) (44).

In the completed cohorts for Arms IV and V, ORR per iRECIST was observed in 11.1% of subjects in Arm IV (3/27 subjects) with 3.7% (1/27 evaluable) achieving confirmed PR per RECIST 1.1 (45), and in Arm V, ORR per iRECIST was achieved in 7.7% of subjects (2/26 evaluable) and RECIST 1.1 was achieved in 3.8% of subjects (1/26 evaluable) (46).

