## V7.0 incorporating Amendment 6, 26Oct2023

**Note:** Subjects with RECIST-defined progressive disease (PD) who are otherwise stable without symptomatic progression should continue study treatment until the next radiographic imaging time point (at least 4 weeks after the prior assessment of PD) to assess for possible pseudo-progression.

Discontinuation from treatment does not represent withdrawal from the trial.

Subjects may discontinue treatment at any time for any reason or be dropped from treatment at the discretion of the Investigator, should any untoward effect occur. In addition, a subject may be discontinued from treatment by the Investigator or the Sponsor, if treatment is inappropriate, the trial plan is violated, or for administrative and/or other safety reasons.

A subject may be discontinued from treatment but continue to be monitored in the trial for any of the following reasons:

- The subject or subject's legally acceptable representative requests to discontinue treatment
- The Investigator believes that for safety reasons or tolerability reasons (e.g., AE) it is in the best interest of the subject to discontinue study drug.
- Intercurrent illness that prevents further administration of treatment
- Unacceptable AEs (e.g., those meet the DLT criteria or other adverse events which can jeopardize patient safety per enrolling physician or considered unacceptable by the subject)
- Progressive disease confirmed radiographically.
  - *Note: In the case of suspected pseudoprogression, patients will be advised to continue treatment beyond initial RECIST 1.1-defined PD while waiting for confirmation of PD, provided they are clinically stable (per iRECIST). Investigators are recommended to consult with the Sponsor designee regarding individual cases.*
  - Treatment interruption lasting >12 weeks (see Section [8.1.1](#))
  - The patient becomes pregnant. Refer to Section [11.8](#).
  - Noncompliance with study procedure requirements or study drug administration (e.g., non-compliance with study visits and miss too many drug administrations).
  - The subject persistently uses a disallowed medication as discussed with the Sponsor's designee.
  - Discontinuation of treatment may be considered, at the discretion of the treating physician per criteria below, but continue to be monitored in the study for any of the following reasons:
    - Recurrent Grade 2 pneumonitis

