### 13.2. Tumor Imaging During the Study

The first on-study imaging assessment should be performed at 6 weeks ( $\pm 1$  week) from the date of the first study treatment. Subsequent tumor imaging should be performed every 6 weeks ( $\pm 1$  week) or more frequently if clinically indicated. After the first 6 months, subjects who remain on treatment will have imaging performed every 9 weeks ( $\pm 1$  week). Imaging timing should follow calendar days and should not be adjusted for delays in cycle start dates. Imaging should continue to be performed until disease progression is identified by the investigator, or notification by the Sponsor, whichever occurs first.

Brain MRI is required during the study only if:

- The screening brain scan is positive (has tumor lesion)
- The subject develops sign/symptoms suggestive of brain metastasis

Brain CT imaging is acceptable if MRI is medically contraindicated or cannot be scheduled in a timely manner.

Objective response should be confirmed by a repeat imaging assessment. Tumor imaging to confirm PR or CR should be performed at least 4 weeks after the first indication of a response is observed. Subjects will then return to regular scheduled imaging, starting with the next scheduled imaging time point. Subjects who receive additional imaging for confirmation do not need to undergo the next scheduled tumor imaging if it is less than 4 weeks later; tumor imaging may resume at the subsequent scheduled imaging time point.

Per iRECIST ([Appendix A – Assessment of Disease](#)) disease progression should be confirmed by the site, 4 to 8 weeks after site-assessed first radiologic evidence of PD in clinically stable subjects. Subjects, who have unconfirmed disease progression may continue on treatment at the discretion of the investigator until progression is confirmed by the site, provided they have met the conditions detailed in [Appendix A – Assessment of Disease](#). Subjects who receive confirmatory imaging do not need to undergo the next scheduled tumor imaging if it is less than 4 weeks later; tumor imaging may resume at the subsequent scheduled imaging time point, if clinically stable. Subjects, who have confirmed disease progression by iRECIST, as assessed by the site, will discontinue study treatment. Exceptions are detailed in [Appendix A – Assessment of Disease, Table 6](#).

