#### 13.4.3. Evaluation of Best Overall Response

The best overall response is the best response recorded from the start of the treatment until disease progression/recurrence (taking as reference for progressive disease the smallest measurements recorded since the treatment started). The subject's best response assignment will depend on the achievement of both measurement and confirmation criteria.

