## For Subjects with Measurable Disease (i.e., Target Disease)

Target Lesions	Non-Target Lesions	New Lesions	Overall Response	Best Overall Response when Confirmation is Required*
CR	CR	No	CR	>4 wks. Confirmation**
CR	Non-CR/Non-PD	No	PR	>4 wks. Confirmation**
CR	Not evaluated	No	PR	
PR	Non-CR/Non-PD/not evaluated	No	PR	
SD	Non-CR/Non-PD/not evaluated	No	SD	Documented at least once >4 wks. from baseline**
PD	Any	Yes or No	PD	no prior SD, PR, or CR
Any	PD***	Yes or No	PD	
Any	Any	Yes	PD	

\* See RECIST 1.1 manuscript for further details on what is evidence of a new lesion.

\*\* Only for non-randomized studies with response as primary endpoint.

\*\*\* In exceptional circumstances, unequivocal progression in non-target lesions may be accepted as disease progression.

*Note: Subjects with a global deterioration of health status requiring discontinuation of treatment without objective evidence of disease progression at that time should be reported as "symptomatic deterioration." Every effort should be made to document the objective progression even after discontinuation of treatment.*

Abbreviations: CR=complete response; PD=progressive disease; PR=partial response; RECIST=Response Evaluation Criteria in Solid Tumors; SD=stable disease.

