1.2.2 Secondary Endpoints

Phase 1b/2a/Biomarker Cohort:

- ORR (Biomarker Cohort only) defined as the percentage of subjects who have at least one confirmed PR or CR, per by RECIST 1.1 and iRECIST as determined by the investigator.

Confidential

- DoR for the responders in each individual arm, defined as the time from the first occurrence of a documented objective response to the time of the first documented disease progression or death from any cause, whichever occurs first, per RECIST 1.1 and iRECIST as determined by the investigator.
- DCR for each individual arm, defined as proportion of subjects with a best overall response (BOR) of CR, PR or SD, per RECIST 1.1 and iRECIST as determined by the investigator.
- PFS for each individual arm, defined as the time from the first study treatment (Cycle 1, Day 1) to the first occurrence of disease progression or death from any cause, whichever occurs first, per RECIST 1.1 and iRECIST as determined by the investigator.
- OS for each individual arm, defined as the time from first study treatment (Cycle 1, Day 1) to death from any cause.
- Incidence of anti-drug antibody (ADA) to NT-I7 during the study relative to the prevalence of ADA at baseline.

Biomarker Cohort:

- Incidence, nature, and severity of AEs graded according to NCI CTCAE v5.0.

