4.9.4.2 Disease Control Rate per investigator

DCR per RECIST 1.1 is defined the proportion of subjects with confirmed CR, confirmed PR, SD (minimum duration of 4 weeks from the first dose of study drugs to the date of last non PD/NE) as BOR in efficacy evaluable analysis set.

iDCR per iRECIST is defined the proportion of subjects with iCR, iPR, iSD as iBOR in efficacy evaluable analysis set.

Exact two-sided 95% CIs for the DCR/iDCR will be calculated using Clopper-Pearson method.

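### SAP 4.9.2 does not stop RECIST 1.1 best overall response at first progression, and its Unknown category overlaps Table 3

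*SAP*

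**What the plan says.** **BOR window.** Protocol 13.4.3: "The best overall response is the best response recorded from the start of the treatment until disease progression/recurrence". Its table for measurable disease attaches to an overall response of PD the condition "no prior SD, PR, or CR". SAP 4.9.2: "BOR will be derived based on all overall visit response per subject". The SAP repeats that sentence at the start of its iRECIST subsection, 4.9.2.2.

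**Visits after progression.** Protocol 13.2: "Subjects, who have unconfirmed disease progression may continue on treatment at the discretion of the investigator until progression is confirmed by the site". Protocol 6.4.1 says that subjects with RECIST-defined PD who are otherwise stable "should continue study treatment until the next radiographic imaging time point (at least 4 weeks after the prior assessment of PD"). SAP 4.9.1 has the investigator report the overall response at each visit under both criteria.

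**Endpoints built on BOR.** SAP 4.9.3 defines RECIST 1.1 ORR as the proportion with confirmed CR or PR as BOR. SAP 4.9.4.2 counts in DCR "SD (minimum duration of 4 weeks from the first dose of study drugs to the date of last non PD/NE) as BOR". SAP 1.2.2 defines DoR as "the time from the first occurrence of a documented objective response to the time of the first documented disease progression" or death.

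**Unconfirmed iCR/iPR.** SAP 4.9.2.2 first applies Table 3 to iRECIST, reading PD as iUPD. The last bullet of the same list assigns an unconfirmed iCR or iPR, or an iSD shorter than 4 weeks, to a category called Unknown.

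**The concern.** RECIST 1.1 and iRECIST need different visit windows. Using visits after first RECIST 1.1 PD is proper for iRECIST, but under Protocol 13.4.3 it is not proper for RECIST 1.1. The SAP gives one all-visits sentence for both. Nothing else in the SAP restores the stop: Table 3 has no row starting from PD, the ORR definition has no before-PD condition, the last non-PD/NE date in the DCR rule may fall after a PD, and SAP section 6 declares no change to BOR.

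What is at stake is an upward bias in RECIST 1.1 ORR, a primary endpoint with its own test, and in RECIST 1.1 DCR.

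The Unknown bullet is a separate and smaller matter. It can remove from iDCR a subject whom Table 3 counts as iSD, although Appendix A says there is no separate iRECIST assessment before RECIST 1.1 progression. iORR, the iRECIST-based Go/No Go decision and the design figures are not affected by either point.

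**Working it through.** **1. Scan sequences under each rule.**

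| Scans | Protocol 13.4.3 | SAP read literally |
|---|---|---|
| PD wk 6, PR wk 12, PR wk 18 | BOR is PD; not in ORR | Table 3, PR then PR, 6 weeks apart (at least 4 needed): confirmed PR, in ORR |
| PD wk 6, SD wk 12 | BOR is PD; not in DCR | Last non-PD/NE visit is 12 weeks from first dose (at least 4 needed): SD, in DCR |

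For the first subject, DoR would start at week 12 and end at the first PD at week 6: 6 − 12 = −6 weeks. The miscount needs a post-PD visit recorded as non-PD under RECIST 1.1. That mainly means target-lesion pseudo-progression, because in the protocol's table a persisting new lesion keeps the visit at PD.

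**2. The Unknown overlap.** Take PR at week 6, SD at week 12 and no later response.
- RECIST 1.1, Table 3: PR then SD gives SD, counted in DCR.
- iRECIST, imported Table 3: iSD, counted in iDCR.
- iRECIST, last bullet: unconfirmed iPR gives Unknown, not counted in iDCR.

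The 4-week minimum (which Table 3 does not attach to PR then SD) rarely separates the two rules. The first scan is due at week 6 ± 1, so an on-schedule scan is no earlier than week 6 − 1 = 5. A response with no later scan has no row in Table 3, and there Unknown fills a real gap.

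**3. The plan's own design figure.** Inputs from Protocol 15.1 and SAP 1.4: 17 + 8 = 25 evaluable, null 4%, alternative 21%, one-sided alpha 0.025, power 80%. Stage 1 stops at 0 responders. The final boundary is not stated in the documents; it is derived here. With X1 ~ Bin(17, p) and X2 ~ Bin(8, p),

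P(reject) = Σ over x1 = 1 to 17 of P(X1 = x1) · P(X2 ≥ c − x1).

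- c = 3: alpha 0.0749, power 0.916.
- c = 4: alpha 0.0164, power 0.800.

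So at least 4 of 25 is the largest region within 0.025, and the stated 80% power is reproduced.

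**4. Effect of one subject at the boundary.** Exact one-sided binomial P(X ≥ x | 25, 0.04), with Clopper-Pearson 95% limits:
- 3/25: p = 0.0765, CI 2.55% to 31.22%.
- 4/25: p = 0.0165, CI 4.54% to 36.08%.

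One PD-first subject counted as PR takes 3 true responders across 0.025 and lifts the lower limit above 4%. The binomial chance of exactly 3/25 is 6.0%, 18.0%, 23.6% and 11.9% at a true ORR of 4%, 7.7%, 11.1% and 21%.

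**5. Effect on the error rate.** The documents give no rate m of PD-first confirmed PR, so m is an assumption. The formula in step 3, with c = 4 and p = 4% + m, gives:
- m = 0: 0.016
- m = 1 point: 0.034
- m = 2 points: 0.060
- m = 4 points (1/25 = 4%): 0.135

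This applies the RECIST 1.1 rate to a stage 1 stop that is decided on iRECIST. At m = 0 the effect is negligible: without the stop the figure is 0.0165 instead of 0.0164.

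**6. Data already reported.** Protocol 2.3 states: "ORR per iRECIST was observed in 11.1% of subjects in Arm IV (3/27 subjects) with 3.7% (1/27 evaluable) achieving confirmed PR per RECIST 1.1". For Arm V it gives 2/26 by iRECIST and 1/26 by RECIST 1.1. As an upper bound, suppose every extra iRECIST responder were a PD-first subject counted under RECIST 1.1:
- Arm IV: 1/27 (p = 0.668) becomes 3/27 (p = 0.092).
- Arm V: 1/26 (p = 0.654) becomes 2/26 (p = 0.279).

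Neither reaches 0.025.

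**The case against.** The SAP says it is based on Protocol V7.0 and declares no BOR change, so the protocol's stop arguably governs, and the all-visits sentence may only mean that BOR is built from visit-level responses. Table 3 is a confirmation table, with no SD-first row either, so the missing PD-first row proves little. The literal reading gives a negative DoR. It would also largely merge ORR with iORR, since the two criteria separate only after RECIST 1.1 PD. The lower RECIST 1.1 counts in Protocol 2.3 suggest that post-PD responses are not being counted. The route to a miscount is narrow and its rate is assumed. On the second point, Unknown comes last in its list and reads naturally as a residual category, affecting only a descriptive secondary endpoint.

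Much of this stands. A stop at PD is probably intended, the size is hypothetical, and part of the gap in Protocol 2.3 may reflect confirmation status. It does not remove the problem. The all-visits sentence is a stated rule on a primary endpoint that differs from the protocol, and planned post-PD scans supply the visits it would use. In 4.9.2.2 the sequential wording governs only the iCPD/iUPD bullet. Nothing ranks Unknown below Table 3.

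**Conclusion.** Both points hold as defects of SAP wording. Neither shows that a result is wrong. Followed literally, the SAP could count a PD-first subject as a RECIST 1.1 responder or as disease control, and each such subject moves ORR or DCR by 4 points at n=25. One is enough to turn 3/25 into a rejection at 4/25. Any inflation of the error rate above 0.016 depends on the assumed m. For Arms IV and V no reported conclusion changes, even at the upper bound. The Unknown overlap affects iBOR and iDCR only, by the same 4 points per subject, and only for sequences that Table 3 covers. The wording should be corrected, because a primary endpoint should not depend on a programmer inferring the intended window.

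**What to change.** - **SAP 4.9.2.1:** derive RECIST 1.1 BOR only from assessments up to and including the first RECIST 1.1 PD, in line with Protocol 13.4.3. Keep the all-visits sentence for iRECIST.
- **SAP 4.9.4.2:** measure SD to the last non-PD/NE assessment before first PD.
- **SAP 4.9.2.2:** apply Table 3 first. Limit Unknown to cases Table 3 does not cover, such as a response with no later scan, or that fail the 4-week minimum.
- **SAP section 6:** if the all-visits rule is intended for RECIST 1.1, list it as a change from the protocol.

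The cost is SAP wording and programming, with no new data. RECIST 1.1 ORR and DCR may come out slightly lower than under the literal wording. Sample size and power do not change.

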4.9.2.1 Best Overall Response per RECIST 1.1

The derivation rules of confirmed response in table 3 are listed for RECIST 1.1.

Table 3 Derivation of Confirmation of Response from Timepoint Overall Response

Response at First Time Point	Response at Subsequent Time Point	BOR with Confirmation per RECIST 1.1
CR	CR	CR
CR	PR	SD, PD, or PR ^a
CR	SD or PD	SD provided minimum criteria ^b for SD duration met, otherwise PD
CR	NE	SD provided minimum criteria ^b for SD duration met, otherwise NE
PR	CR or PR	PR
PR	SD	SD
PR	PD	SD provided minimum criteria ^b for SD duration met, otherwise PD
PR	NE	SD provided minimum criteria ^b for SD duration met, otherwise NE

BOR = best overall response; CR = complete response; PR = partial response; SD = stable disease, PD = progressive disease; NE = not evaluable.

^a If a CR is truly met at first time point, then any disease seen at a subsequent time point, even disease meeting PR criteria relative to baseline, makes the disease PD at that point (since disease must have reappeared after CR). Best response would depend on whether minimum duration for SD was met. However, sometimes ‘CR’ may be claimed when subsequent scans suggest small lesions were likely still present and in fact the subject had PR, not CR at the first time point. Under these circumstances, the original CR should be changed to PR and the best confirmed response is PR.

^b Minimum criteria for SD duration is 4 weeks.

A BOR of CR or PR must be confirmed by a tumor assessment that should be performed no less than 4 weeks after the criteria for response are first met. One intervening response SD is allowed for PR confirmation (PR SD PR=PR; PR SD CR=PR if confirmed CR is not achieved).

4.9.2.2 Best Overall Response per iRECIST

BOR will be derived based on all overall visit response per subject. The iRECIST assessment has the following possible response categories: iCR, iPR, iSD, immune-Unconfirmed PD (iUPD), immune-Confirmed PD (iCPD) or immune-Not Evaluable (iNE). The iRECIST criteria is similar to RECIST v1.1 but for PD, iRECIST requires an evaluation of PD to be confirmed at subsequent assessment. For purposes of iRECIST assessment, the first visit showing PD according to RECIST v1.1 will be assigned as Immune-Unconfirmed PD (iUPD) at this visit. Additional imaging for confirmation should be scheduled 4 to 8 weeks from the imaging on which iUPD is seen. This may correspond to the next visit in the original visit schedule. The assessment of the subsequent confirmation imaging proceeds in an identical manner, with possible outcomes of iCPD, iUPD, and iSD/iPR/iCR.

BOR (when confirmation required) per iRECIST will be derived as follows:

- BOR follows the same rules as table 3 per RECIST for confirmation of iCR/iPR, and iSD (meet the minimum criteria), except PD in column response at subsequent

timepoint in table 3 per RECIST is considered as iUPD and should be confirmed by iCPD.

- BOR of iPd (iCPD>iUPD):
 - If subjects did not meet BOR of iCR/iPR, and iSD, BOR for iCPD (time point iUPD must be confirmed by timepoint iCPD no less than 4 weeks per iRECIST) can be achieved as order of iUPD followed by iCPD without interruption of iCR, iPR, iSD.
 - If above scenarios are not achieved, BOR is identified as iUPD.
- BOR of NE refers to no baseline or no postbaseline assessments or all postbaseline assessments are NE.
- BOR of Unknown refers to unconfirmed iCR/iPR or early iSD <4 weeks from first dose date.

